2.3.1 Alkaline Phosphatase

ALP results are provided by the central and local laboratory with units of Units per Liter (U/L). Baseline is defined as the last available ALP result prior to treatment with change from baseline and percent change from baseline based upon this baseline value as the respective timepoint. Normalized ALP is defined as having ALP within the normal range (37 U/L to 116 U/L). Historical ALP will be summarized in the baseline characteristics table but not used otherwise.

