## **9. STUDY ASSESSMENTS AND PROCEDURES**

### **9.1. Efficacy Assessments**

#### **9.1.1. Serum Alkaline Phosphatase Endpoints**

The ALP endpoints including the primary endpoint are based upon laboratory results. Results will be assigned to time points based upon the timing of the sample. Baseline will be the last available ALP result available prior to treatment with HTD1801 and change from baseline and percent change will be based upon this baseline value and the value as the respective timepoint. The binary  $\geq 20\%$  and  $\geq 40\%$  decrease endpoints will be based upon the percent change from baseline measure (did or did not have a percent change of this size). The normalization of ALP endpoint will be based upon the result and the associated normal range provided by the laboratory.

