### **11.2. Operational Contingencies related to COVID-19 Pandemic**

Local site policies and process for COVID-19 monitoring, for example, temperature check, COVID-19 exposure history, recent travel history and use of personal protective equipment must be followed.

The study protocol specifies that all visits are in-clinic visits but allows for contingency measures for Study Visits Week 2, 4, 8, 16 and the Early Termination visit in the occurrence where a subject is unwilling or unable to participate in an in-clinic visit due to the COVID-19 pandemic.

In that instance, the site will work with the study subject to obtain study-required blood draws at a local laboratory or arrangements will be made to have the home health provider obtain the visit specific blood draw for the study-required laboratory assessments.

Other visit assessments will have to occur via a remote visit by telephone or a video conference, per site practice and procedures, to assess changes in the subjects' health condition, make note of any changes in concomitant medications, and inquire about adverse events. The visit must be documented as a telephone/video conference visit with arrangements for laboratory assessments.

The site will enter the laboratory results, if obtained at a local laboratory, into the EDC as an "unscheduled" visit that will be mapped to the specific visit for which local laboratory data were obtained. If the visit specific blood draw is obtained by the home health service provider, it will be shipped to the central laboratory; the results will be entered into the central laboratory database and merged with the clinical database at the completion of the study.

Every effort must be made to complete the full scope of the study visit activities and procedures. Any deviation from the procedures and protocol-specified contingency measures due to COVID-19 must be clearly documented as COVID-19-related and reported to the IRB as applicable.

The PI and study personnel are responsible for ensuring full investigational product accountability.

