2.3 Study Endpoints

The study endpoints are listed below, with greater detail concerning these endpoints provided in Sections 2.3.1 to 2.3.8.

Primary Efficacy Endpoint

The primary efficacy endpoint is the percent change in ALP at Week 12 compared to Baseline.

ALP Secondary Efficacy Endpoints

The ALP secondary efficacy endpoints are as follows:

- Absolute change in serum ALP at Week 12 compared to Baseline
- Proportion of subjects who have $\geq 20\%$ decrease in ALP from Baseline to Week 12
- Proportion of subjects who have $\geq 40\%$ decrease in ALP from Baseline to Week 12
- Proportion of subjects who normalize ALP at Week 12

Secondary Endpoints

- Change in total bilirubin from Baseline to Week 12
- Change in serum GGT between Baseline and Week 12
- Change in alanine aminotransferase (ALT) from Baseline to Week 12
- Change in aspartate aminotransferase (AST) from Baseline to Week 12
- Change in total cholesterol, low-density lipoprotein (LDL) cholesterol, and triglyceride levels between Baseline and Week 12
- Change in fibrinogen, c-reactive protein (CRP), haptoglobin, enhanced liver fibrosis (ELF) score, and serum immunoglobulins between Baseline and Week 12

Safety endpoints include the following:

- Changes from Baseline to Week 6 and Week 12 in GLOBE Score

HighTide Biopharma Pty. Ltd.
Protocol HTD1801.PCT013

- Changes from Baseline to Week 6 and Week 12 in pruritus (average and worst) as measured by pruritus visual analog score (VAS)
- Changes from baseline in vital signs, and clinical laboratory values
- Incidence of treatment-emergent adverse events (TEAEs) and serious adverse events (SAEs)
- PK parameters including $T_{1/2}$, C_{max} , and AUC
 - The analysis of these PK endpoints will be performed outside of this analysis plan.

Additional Analyses

- Proportion of subjects who have $\geq 10\%$ decrease in ALP from Baseline to Week 12
- Proportion of subjects at Week 12 who had Baseline ALP $\geq 1.67 \times$ ULN and have ALP $< 1.67 \times$ ULN, $\geq 15\%$ decrease in ALP and total bilirubin \leq ULN at Week 12.
- A plot of percent change in ALP at each timepoint through Week 12 for the ratio of current to prior dose of UDCA
- Proportion of subjects that crossed the liver monitoring thresholds will be summarized. The liver monitoring threshold is defined as ALT:
 - 3x ULN if the Baseline ALT is ≤ 60 U/L, or
 - 3x Baseline ALT if Baseline ALT is > 60 U/L

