The proportion of subjects who have $\geq 20\%$ and the proportion with a $\geq 40\%$ decrease in ALP from Baseline will be summarized at each timepoint with Week 12 being the study specified timepoint. Additionally, the proportion of subjects who normalize ALP will be summarized by timepoint.

3.3.2 *Secondary Endpoints*

Tables for the secondary endpoints, see below, will be summarized for the respective laboratory values and the change from baseline results at each timepoint. Total bilirubin and GGT will be summarized within the ITT and PP populations. Subgroup analyses for specified laboratory parameters (see section 2.5.2) will be performed for the change from baseline and percent change at Week 12. Central and local lab data will be used for the efficacy analyses.

- Total bilirubin
- GGT
- ALT
- AST
- Total cholesterol

- LDL
- Triglyceride
- Fibrinogen
- CRP
- Haptoglobin
- ELF
- Immunoglobulins (IgM and IgG)

3.3.3 *UDCA Use*

A plot of average percent change in ALP at each timepoint through Week 12 for groups defined by the ratio of current to prior dose of UDCA. The ratio groups displayed in the plot will be <90%, 90% to 110%, and >110%. Separate subject level plots will also be presented for each ratio group through Week 12.

3.3.4 *ELF Score*

The number of subjects within ELF score interpretations will be presented at Week 12 as well as the shift within categories for change from baseline to week 12. Summary statistics at Week 12 will also be presented.

3.3.5 *GLOBE Score*

The number of subjects within GLOBE score interpretations will be presented along with the Fibrosis Score interpretations. Change in GLOBE score from baseline will be summarized using descriptive statistics at Week 6 and Week 12. A listing of the GLOBE score will also be produced and summarized by duration of UDCA exposure.

Survival risk (%) for 5, 10, and 15 years will be summarized using descriptive statistics at Week 12 for the GLOBE Scores.

3.4 *Analysis of Safety Endpoints*

Safety Endpoints (Adverse Events, Clinical Laboratory Results, Vital Signs) will be presented at the scheduled timepoints as outlined in Table 1, with further detail in the protocol.

3.4.1 *Adverse Events*

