3.4.1.1 Post-Treatment Withdrawal Flares

The difference between Week 12 and Week 16 laboratory values for ALP, ALT, AST, and GGT will be summarized using descriptive statistics.

3.4.2 *Pruritus VAS*

Change in Pruritus VAS will be summarized using descriptive statistics for the result and change from baseline. The proportion of subjects with improvement will be presented for subjects $>0.5\text{cm}$ at baseline. The proportion of subjects with worsening will be presented for subjects $\leq 0.5\text{cm}$ at baseline.

3.4.3 *Clinical Laboratory Evaluations*

Clinical laboratory results, including bile acids, will be summarized by type of laboratory assessment (hematology, serum chemistry, lipids, coagulation, other) and timepoint. Both central and local laboratory results will be used for the safety lab summaries. Summary statistics for actual values and changes from baseline will be tabulated by analysis window. Out of range clinical laboratory values based upon the normal range will be tabulated for each timepoint. These tables will utilize the normal ranges provided for the individual sample.

The proportion of subjects that cross the liver monitoring thresholds will be summarized. A listing of ALT values for subjects that meet the liver monitoring threshold will be presented similarly to the clinical laboratory listing. Baseline values will be summarized using last available measurement prior to administration of study drug.

3.4.4 *Vital Signs*

The observed data at baseline and change from baseline for each measurement day will be summarized with descriptive statistics.

3.4.5 *Electrocardiogram Results*

The overall ECG assessment (abnormal or normal) will be summarized by analysis window. The QT values will be summarized by analysis window as both the QT value and change from baseline.

3.4.6 *Pregnancy*

A listing of positive pregnancy tests results will be produced.

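### SAP 2.3.1 judges ALP normalisation against one fixed range although local-laboratory results are pooled in, whereas Protocol 9.1.1 and SAP 3.4.3 use the range that comes with the result

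*SAP*

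**What the plan says.** **Protocol 9.1.1 (Serum Alkaline Phosphatase Endpoints):** "The normalization of ALP endpoint will be based upon the result and the associated normal range provided by the laboratory".

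**SAP 2.3.1 (Alkaline Phosphatase):** "ALP results are provided by the central and local laboratory with units of Units per Liter (U/L"). The same paragraph then sets the criterion: "Normalized ALP is defined as having ALP within the normal range (37 U/L to 116 U/L"). It makes no exception for local results and does not say whose range this is.

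**SAP 3.3.2 (Secondary Endpoints):** "Central and local lab data will be used for the efficacy analyses".

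**SAP 3.4.3 (Clinical Laboratory Evaluations), on the out-of-range safety tables:** "These tables will utilize the normal ranges provided for the individual sample".

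**The endpoint.** SAP 2.3 lists it among the secondary ALP endpoints: "Proportion of subjects who normalize ALP at Week 12". SAP 3.3.1 extends the reporting to other visits: "Additionally, the proportion of subjects who normalize ALP will be summarized by timepoint".

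**Where local results can arise.** Protocol 11.2 "allows for contingency measures for Study Visits Week 2, 4, 8, 16 and the Early Termination visit", and the blood draw may then be done at a local laboratory, with the result mapped to the scheduled visit. Protocol Tables 7 and 8 allow local draws for unscheduled liver monitoring.

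**The concern.** The protocol and the SAP give different rules for the same binary secondary endpoint, and the SAP applies two rules to one analyte. A local result would be held against a limit that may belong to another laboratory. If the local upper limit is above 116 U/L, a value between the two is normal for that laboratory but counted as not normalised. If it is below 116 U/L, a value between the two is abnormal for that laboratory but counted as normalised.

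The SAP flags other departures: it labels its additional analyses as extensions of the protocol endpoints (2.3) and comments on differing baseline definitions (2.4.1). It flags nothing here, so the fixed range does not read as a recorded change. The protocol itself warns, in inclusion criterion 4c, that ALP reference ranges can vary considerably; it says so of the historical value.

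**Working it through.** **1. The rules side by side.**

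| Place | Results covered | Range applied |
|---|---|---|
| Protocol 9.1.1 | ALP endpoints | the one the laboratory supplies with the result |
| SAP 2.3.1 | central and local ALP | 37-116 U/L |
| SAP 3.4.3 | central and local safety laboratory values | the individual sample's |

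Nothing in either document rescales local values to the central range or restricts normalisation to central results. SAP 2.3.2 labels its own ranges as the central laboratory's. That 37-116 U/L is also central is an inference.

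**2. Exposure by visit.** The local-laboratory contingency covers Weeks 2, 4, 8, 16 and early termination. Weeks 2, 4 and 8 are on treatment and enter the by-timepoint summaries directly. Week 12 is not on the list. A local value can reach the Week 12 window (SAP Table 2: Days 71-90, no more than one day after the last dose) in three ways: an on-treatment early-termination sample, an unscheduled local draw, or a sample sent locally under Protocol 10.1.3. That section names Week 12 and speaks of a central or local laboratory. Where several results fall in the window, SAP 2.4 keeps the one nearest Day 84.

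**3. The plan's own design figure.** Protocol 12.2 states at least 90% power with 30 subjects, mean reduction 15%, SD 25% and one-sided 5%. With 29 degrees of freedom and noncentrality (15/25) × √30 = 3.286, the one-sample t-test has 94.1% power, so the statement is reproduced. Percent change does not use the normal range, so this figure is unaffected.

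**4. Weight of one subject.** 1/30 = 3.3 points; with 25 subjects with data, 1/25 = 4.0 points.

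**5. Illustration under assumed local limits.** The documents give none, so upper limits of 100 to 150 U/L are an assumption. Take percent change as normal with the plan's mean of -15% and SD of 25%, hold the measured value fixed whichever laboratory's limit is applied, and ignore the lower limit. Then

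P(normalise) = Φ{[100 × (U - B)/B + 15]/25},

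with upper limit U and baseline B. If 116 U/L is the upper limit that applies, the entry threshold is 1.5 × 116 = 174 U/L. For B = 174 and U = 116: (-33.3 + 15)/25 = -0.73, giving 23.2%.

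| Upper limit (U/L) | B = 174 | B = 232 (2 × 116) |
|---|---|---|
| 100 (assumed) | 13.5% | 4.7% |
| 116 (SAP) | 23.2% | 8.1% |
| 120 (assumed) | 26.1% | 9.2% |
| 130 (assumed) | 34.0% | 12.3% |
| 150 (assumed) | 51.9% | 20.8% |

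For a threshold subject whose sample is local, the shift from the fixed-range value runs from -9.6 to +28.8 points. These are probabilities for one such subject. They do not estimate the bias in the trial, which also depends on the unknown number of local samples.

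**The case against.** The strongest reply is that the named endpoint is hardly touched. It is defined at Week 12, which is a clinic visit (Protocol 8.7) outside the local-laboratory contingency, and the nearest-to-Day-84 rule normally favours the scheduled sample. Protocol 9.2.6 assigns the scheduled safety laboratory tests to a central laboratory, and home-health draws are shipped there too (11.2). The central-or-local wording of Protocol 10.1.3 sits in a section on ALT monitoring. All of this stands, and it limits the point mainly to the Week 2, 4 and 8 summaries. It does not close Week 12 completely.

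It can also be said that Protocol 9.1.1 refers to the laboratory in the singular, so the SAP may only be writing out the central range. That is possible, but the SAP pools local results in the same paragraph and says nothing about how to classify them. Reading the protocol as the range attached to each result is the more natural reading.

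A reader might also infer that counting ALP below 37 U/L as not normalised departs from the protocol. It does not: Protocol 9.1.1 also speaks of a normal range, not of being at or below the upper limit. The effect is negligible as well. From 174 U/L it takes a fall of (174 - 37)/174 = 79%, with probability Φ[(-78.7 + 15)/25] of about 0.5% under the plan's assumptions.

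**Conclusion.** The inconsistency is real, and SAP 2.3.1 followed as written can misclassify local ALP results lying between 116 U/L and the local upper limit. The consequence is limited: the endpoint is secondary and descriptive, and the exposure is mainly at supportive timepoints.

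A reader might infer that the Week 12 normalisation proportion will be materially biased. The documents do not support that. They give no local ranges and no count of local samples, and the number reclassified at Week 12 could be zero. What can be said is 3.3 points per reclassified subject at n = 30, in either direction. The larger figures in the illustration rest entirely on the assumed limits of 100 to 150 U/L.

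A reader might also take the SAP's additional responder analysis at 1.67 × ULN to be wrong for the same reason. There the SAP only leaves unsaid which upper limit applies; it does not state a conflicting rule.

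**What to change.** In SAP 2.3.1, define normalised ALP as a result within the normal range supplied with that sample, in line with Protocol 9.1.1 and SAP 3.4.3. State whose range 37-116 U/L is, and that it applies only to samples from that laboratory.

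The cost is about one sentence in the SAP and a small programming change. No new data are needed, because the safety tables already call for sample-level ranges. If the sponsor prefers the fixed range, the SAP should record it as a deliberate change from the protocol and add a sensitivity analysis using sample-specific ranges.

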2.3.2 Liver Laboratory Tests

Total bilirubin, GGT, AST, and ALT results are provided by the central and local laboratory. The units these parameters are provided in and the normal range for these parameters at the central laboratory are provided below.

HighTide Biopharma Pty. Ltd.
Protocol HTD1801.PCT013

Laboratory Test	Units	Normal Range
Total bilirubin	mg/dL	0.25 to 1.21
GGT	U/L	7 to 38
AST	U/L	14 to 43
ALT	U/L	10 to 53

2.3.3 *Lipid Laboratory Tests*

Total cholesterol, low-density lipoprotein (LDL) cholesterol, and triglyceride results are provided by the central and local laboratory. The units these parameters are provided in and the normal range for these parameters are provided below.

Laboratory Test	Units	Normal Range
Total Cholesterol	mg/dL	100 to 200
LDL	mg/dL	50 to 130
Triglycerides	mg/dL	50 to 150

2.3.4 *Serum Markers of Inflammation*

Fibrinogen and c-reactive protein (CRP) results are provided by the central and local laboratory. Haptoglobin and serum immunoglobulins results are provided by the central laboratory. The units these parameters are provided in and the normal range for these parameters are provided below.

Laboratory Test	Units	Normal Range
Fibrinogen	mg/dL	200 to 400
CRP	mg/L	0 to 3
Haptoglobin	g/L	0.3 to 2
Immunoglobulin G	mg/dL	700 to 1600
Immunoglobulin M	mg/dL	40 to 230

2.3.5 *Enhanced Liver Fibrosis Score*

The ELF score is a set of serum markers that consist of hyaluronic acid (HA), tissue inhibitor of metalloproteinases 1 (TIMP-1) N-terminal pro-peptide of type III collagen (PIIINP), and tissue inhibitor of metalloproteinases 1 (TIMP-1) used to predict moderate fibrosis and cirrhosis (Lichtinghagen et al., 2013). Change from Baseline to Week 6 and Week 12 will be presented, along with a shift table for the categorical interpretation. The interpretation of the ELF score is as follows:

- None to mild liver fibrosis: ELF score <7.7
- Moderate liver fibrosis: ELF score ≥7.7 and <9.8
- Severe liver fibrosis: ELF score ≥9.8
- Cirrhosis: ELF score >11.3

HighTide Biopharma Pty. Ltd.
Protocol HTD1801.PCT013

2.3.6 ***GLOBE Score***

The GLOBE score is a validated risk assessment tool, able to accurately stratify PBC patients to high and low risk for future adverse events (AEs), where a higher GLOBE score is considered higher risk (Lammers, 2015). Change from Baseline to Week 6 and Week 12 will be presented, along with a shift table for the categorical interpretation, as well as Survival Risk at 5, 10, and 15 years. The GLOBE score will be calculated using the following algorithm:

$$GLOBE\ Score = 0.044378 \times AAAACC + 0.93982 \times CCC \frac{BBBBBBBBBBBBBBBB}{UUUUUU} + 0.335648 \times CCC \frac{AAUUA}{UUUUU} - \\ 2.266708 \times \frac{AABBBBBBAABBB}{UUUUUU} - 0.002581 \times PPCCCCTTCCCCCTT \frac{CCCCDDCCTT}{CCCCDDCCTT} + 1.216865$$

Age (years): at initiation of UDCA therapy.

Units: Bilirubin (μmol/L or mg/dL), ALP (U/L), Albumin (g/L), Platelets (10⁹/L)

SSDDAAAACCAACCC RRCCTTRR SSCCCCAACC = 1 - BBCCTTCCCCCCCCC SSDDAAAACCAACCC FFDDCCCCCTTCCCCC(CC_{GG}UU_{GG}BB_{GG} SS_{GG}SSBB_{GG})

Baseline survival function = 0.9385 (at 5 years); 0.8429 (10 years); 0.7361 (15 years).

The interpretation is as follows:

- Higher risk: GLOBE score >0.3
- Lower risk: GLOBE score <0.3

2.3.7 ***Pruritus Visual Analog Scale***

The Pruritus VAS is a validated, self-reported, instrument for measurement of itch intensity. It uses a 24-hour recall period and asks subjects to rate the average and worst intensity of their itch on a 10 cm horizontal line ranging from 0 cm (no itch) to 10 cm (worst imaginable itch). Change from Baseline to Week 6 and Week 12 will be presented for subjects with a value of ≤0.5cm at baseline and >0.5cm at baseline. The proportion of subjects with improvement (for subjects >0.5cm at baseline) and worsening (for subjects ≤0.5cm at baseline) will also be presented, along with a shift table for the categorical interpretation. The interpretation for the Pruritus VAS score is as follows:

- No pruritus: VAS=0
- Mild pruritus: VAS <3
- Moderate pruritus: VAS 3 to <7
- Severe pruritus: VAS 7 to <9
- Very severe pruritus: VAS ≥ 9

2.3.8 *Safety Parameters*

The following safety parameters are captured within this study.

2.3.8.1 Adverse Events and Serious Adverse Events

AEs and SAEs will be recorded starting after Screening and at every visit through the Week 16 Follow-Up Visit. An AE is considered treatment emergent, TEAE, if it began after study drug administration.

AEs will be graded for severity using the Common Terminology Criteria for Adverse Events (CTCAE) v5.0 to describe the maximum intensity of the AE. As such, severity will be reported as Mild, Moderate, Severe, Very Severe, Life Threatening or Disabling, Death Related. Causality of an AE will be assessed by the Investigator using the following terms: Possibly Related and Unrelated.

AEs and medical history will be coded using MedDRA version 24.0.

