### **9.2.2. Adverse Events**

Adverse events will be collected from the time at which the potential subject signs the ICF. Subjects will be instructed to report all AEs during the study and will be assessed for the occurrence of AEs throughout the study until at least 30 days after discontinuing the study drug. General and non-leading questions such as "How are you feeling?" should be asked when assessing the occurrence of AEs. The definition, reporting, and recording requirements for AEs are described in Section 9.3.

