**Table 4 Classification of Adverse Events (AEs) by Severity**

Severity a	Definition
Mild AE (Grade 1)	Mild; asymptomatic or mild symptoms; clinical or diagnostic observations only; intervention not indicated.
Moderate AE (Grade 2)	Moderate; minimal, local or noninvasive intervention indicated; limiting age-appropriate instrumental activities of daily living
Severe AE (Grade 3)	Severe or medically significant but not immediately life-threatening; hospitalization or prolongation of hospitalization indicated; disabling; limiting self care activities of daily living
Life-threatening or disabling AE (Grade 4)	Life-threatening consequences; urgent intervention indicated.
Death related to AE (Grade 5)	Death related to AE.

a From Common Terminology Criteria for Adverse Events, Version 5.0

Any AE that changes in severity or grade during a single occurrence of an AE will be recorded in the eCRF at the highest level experienced by the subject.

An AE that is assessed as severe should not be confused with an SAE. Severity is a category used for rating the intensity of an AE (such as mild, moderate, or severe myocardial infarction). However, an AE itself may be of relatively minor medical significance, such as a severe headache. Both AEs and SAEs can be assessed as severe. An AE is considered serious when it meets one of the predefined outcomes described in Section 9.3.2.

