#### **12.4.4. Safety Analyses**

Safety endpoints will be summarized using descriptive statistics.

Treatment emergent adverse events (TEAE), events that start on or after the start of treatment, will be summarized by system organ class and preferred term. Summaries of all TEAEs, treatment emergent SAEs, related TEAEs and TEAEs by severity will be produced.

Laboratory, vital sign, and ECG results will be summarized as continuous measures (e.g., change from baseline). Selected laboratory results will also be summarized as categorical variables (e.g., 'in' versus 'out' of the normal range).

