2.4.1 Definition of Baseline

Unless specified elsewhere, baseline is defined as the last available measurement prior to administration of study drug. For events that occur on the same day as the first administration of study drug (i.e. assessments performed at the Baseline visit), and for which the time of the assessment is not available, the assessment will be classified as pre-treatment, hence baseline. The exception to this rule will be AEs for which the event will be classified as a TEAE.

It should be noted that for the purpose of clinical management, the description of baseline varies in the protocol (e.g. inclusion/exclusion and Drug-Induced Liver Injury Monitoring). For analysis purposes, only the definition above will be used.

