An overview of AEs, which includes subject incidence of TEAEs, treatment-related TEAEs, serious TEAEs, AESIs, TEAEs by CTCAE grade and TEAEs leading to permanent discontinuation of treatment. For TEAEs presented by CTCAE grade, the worst grade during the clinical study will be presented for each subject.

The subject incidence of TEAEs, treatment-related TEAEs and TEAEs leading to permanent discontinuation of treatment will be summarized by system organ class and preferred term.

HighTide Biopharma Pty. Ltd.
Protocol HTD1801.PCT013

TEAEs will also be summarized in a table by CTCAE grade. For TEAEs presented by CTCAE grade, the worst grade for each event during the clinical study will be presented for each subject. A listing for all off-treatment AEs will be presented similarly.

All AEs will be presented as a listing by subject. TEAEs leading to treatment discontinuation will be provided in a separate listing.

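### TEAEs are defined by start date alone, so an adverse event already open at first dose that worsens on HTD1801 can be missing from every TEAE-based summary.

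*SAP*

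**What the plan says.** **Definition of a TEAE.** SAP 2.3.8.1: "An AE is considered treatment emergent, TEAE, if it began after study drug administration". Protocol 12.4.4: "Treatment emergent adverse events (TEAE), events that start on or after the start of treatment". SAP 2.4.1 deals with assessments on the day of first dose whose time is unknown. It treats them as pre-treatment, but adds: "The exception to this rule will be AEs for which the event will be classified as a TEAE". Read together, these bring in the day of first dose and go no further.

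**Recording a change in grade.** Protocol 9.3.3.1, under Table 4: "Any AE that changes in severity or grade during a single occurrence of an AE will be recorded in the eCRF at the highest level" that the subject experienced. SAP 2.3.8.1 likewise grades an AE at its maximum intensity.

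**Start of collection.** Protocol 9.2.2: "Adverse events will be collected from the time at which the potential subject signs the ICF". SAP 2.3.8.1: "AEs and SAEs will be recorded starting after Screening and at every visit through the Week 16 Follow-Up Visit"; protocol 9.3.4 agrees with the SAP. Table 1 of the protocol and Table 1 of the SAP first mark AE monitoring at Baseline.

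**Planned summaries.** SAP 3.4.1: "The subject incidence of TEAEs, treatment-related TEAEs and TEAEs leading to permanent discontinuation of treatment will be summarized", by system organ class and preferred term. A further table gives TEAEs by CTCAE grade. The overview counts TEAEs, related and serious TEAEs, TEAEs by grade and TEAEs leading to permanent discontinuation. It also counts AESIs, without saying that these must be TEAEs. All AEs go into a by-subject listing.

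**The concern.** Safety and tolerability over 12 weeks is a stated objective, and TEAE incidence is its main tabulated output. TEAEs are also one of the few outputs planned for the interim summary when 15 subjects have reached Week 12 (SAP 2.8). With one arm, no comparator would reveal an undercount.

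Under a start-date definition with one record per occurrence, an AE that begins as Grade 1 before dosing and reaches Grade 3 on drug becomes a Grade 3 record with a pre-dose start. It fails the TEAE test, although the part of the event that matters for tolerability happened on treatment. The omission can only lower the counts. Protocol 7.2 requires study drug to be stopped for a related AE of Grade 3 or above, whatever its onset date. A subject stopped for such an event could therefore be absent from the table of TEAEs leading to discontinuation.

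**Working it through.** The plan gives no figure of its own on this point. The check is mainly a reading of the rules in sequence, with one line of arithmetic for scale.

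**Step 1. Can an AE be open at first dose?** It depends on which collection start applies.

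| Source | Collection starts | Longest pre-dose span |
|---|---|---|
| Protocol 9.2.2 | signing of the ICF | 56 days if consent is at pre-screening (Day -56), otherwise 28 |
| Protocol 9.3.4, SAP 2.3.8.1 | after Screening | within the 28-day screening period |
| Table 1 in both documents | first marked at Baseline | the Baseline visit itself |

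Protocol 9.3.1 adds that sites note AEs mentioned at Screening and Baseline. The pool is clearly non-empty under the first two rows. Under the third it may be very small: an event starting on the day of first dose is already a TEAE under protocol 12.4.4 and SAP 2.4.1, which leaves only earlier-onset events reported at Baseline.

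**Step 2. What happens if such an AE worsens on drug?** If it is the same occurrence, protocol 9.3.3.1 gives one record at the highest grade. Nothing in the documents tells the site to open a new record or to date the worsening.

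**Step 3. Does that record meet a TEAE definition?** Its start precedes first dose, so it fails both SAP 2.3.8.1 and protocol 12.4.4. The same-day rule in SAP 2.4.1 does not apply. The missing-date rule in SAP 2.6 does not help either, because the start date is known.

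**Step 4. Where does the event appear?**

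| Output in SAP 3.4.1 | Event included? |
|---|---|
| TEAEs overall, by system organ class and preferred term | no |
| Treatment-related TEAEs | no |
| Serious TEAEs (overview) | no |
| TEAEs by CTCAE grade | no |
| TEAEs leading to permanent discontinuation (table and listing) | no |
| AESI count in the overview | possibly, if gastrointestinal (SAP 2.3.8.2) |
| All-AE listing by subject | yes |

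The listing would show a pre-dose start and the highest grade. From those two fields alone a reader could not tell that the increase came after dosing.

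**Step 5. Scale.** With n treated subjects, k missed subjects lower an incidence by 100 × k/n percentage points.

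- n = 30: k = 1 gives 3.3; k = 2 gives 6.7; k = 3 gives 10.0.
- Interim: at least 15 subjects are treated, so k = 1 gives at most 100 × 1/15 = 6.7.

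The documents give no rate of AEs open at first dose and no rate of worsening among them, so k cannot be estimated.

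**The case against.** The strongest reply is that protocol 9.3.1 already covers the case. It lists exacerbation of a pre-existing condition, including greater frequency or intensity, as an AE in its own right. Worsening of a medical-history condition can therefore enter as a new AE with a post-dose start. This stands, and it removes most long-standing PBC complaints from the gap. A reader might infer that chronic fatigue or itch present at entry would be lost; the documents do not support that. For an event already open as an AE, however, sections 9.3.1 and 9.3.3.1 do not say which rule governs, and sites could record the same course differently. The eCRF completion instructions might settle this, but they are not among the documents.

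A reader might also infer that the event vanishes from all adverse event output. It does not: the all-AE listing holds it, and the AESI count may. Other outputs do not depend on TEAE status: reasons for early termination (SAP 3.2.1), dose interruptions and modifications (SAP 3.2.5), Pruritus VAS change and the laboratory summaries. SAE reporting, the individual stopping criteria and the study pause rule are not restricted to TEAEs either. All of this stands. It limits the consequence, but none of it gives an incidence by preferred term and grade.

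Finally, a reader might set one missed case against the 12% gastrointestinal discontinuation rate quoted from the NASH study (12% × 30 = 3.6 subjects) and call it about a quarter of the signal. That is illustration only. The rate comes from another population, protocol 4.3 reports no such discontinuations in PSC, and nothing shows that even one case would be missed.

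**Conclusion.** The gap is real, and it is narrow. Both definitions rest on start date, and the recording rule can hold a worsened event to its pre-dose start. An AE open at first dose that worsens on HTD1801 can therefore be left out of every TEAE-based summary in SAP 3.4.1. The bias is downward only, at 3.3 percentage points per missed subject with 30 treated; the number missed is unknown.

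The conclusion assumes that AEs are collected before the day of first dose, as protocol 9.2.2 states, and that a site treats the worsening as the same occurrence under 9.3.3.1 and not as a new AE under 9.3.1. If collection effectively begins at Baseline, few events would be affected. The point concerns the completeness of safety tabulation in a descriptive single-arm study; it does not affect the ALP analysis or safety reporting during the trial. It should be corrected because the remedy is small and the ambiguity would otherwise be settled site by site.

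**What to change.** 1. In SAP 2.3.8.1 and protocol 12.4.4, use one definition: a TEAE is an AE that starts on or after first dose, or one that is present before first dose and increases in severity on or after it. This also aligns the SAP's wording with the protocol on same-day events.
2. In protocol 9.3.3.1, state that worsening after first dose of an AE already open is recorded with its own date and grade, for example as a new record. Without that date the second limb cannot be programmed. It also brings 9.3.1 and 9.3.3.1 into agreement.
3. Reconcile the start of AE collection across protocol 9.2.2, protocol 9.3.4, SAP 2.3.8.1 and the two schedule tables.

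The cost is two sentences and an eCRF completion note, plus the reconciliation of the collection start. TEAE counts may rise slightly. Sample size, visits and the efficacy analysis are unchanged.
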